### 1.3.2 Dose

The 2% dose was selected for this study based on its widespread use in clinical practice in a variety of antifungal products already approved by FDA, and the larger zones of inhibition of 2% compared with 1% miconazole when incubated with two organisms commonly associated with otomycosis (*Candida albicans* and *Aspergillus niger*) in a sponsor-conducted study *in vitro*. The use of 5 drops of product (at ~30 mg per drop) is based on the estimated volume of the human external ear canal, and the amount believed to be needed to fully coat the canal. The 5 drops planned for this study is the same as that used for DermOtic in the treatment of chronic eczematous external otitis. It is noted that the dose regimen for Floxin™ otic solution (0.3% ofloxacin), an FDA-approved product for the treatment of bacterial otitis externa, is 10 drops in adults and children >13 years. Floxin is aqueous and may not adhere as well to the ear canal as the oil-based miconazole oil. The twice-daily dosing was selected based on evidence that miconazole may not maintain bioactivity in the stratum corneum for a full 24 hours [[Pershing 1994](#)].

### 1.3.3 Inclusion of Subjects with Peanut Allergy

Miconazole oil contains refined peanut oil. Inclusion in this study of subjects with peanut allergy is justified by studies and publications documenting safe use of the refined peanut oil, as well as products containing the refined peanut oil (such as DermOtic, which is the same product as the Derma-Smoothe/FS for which two safety studies were performed in subjects with known hypersensitivity to peanuts) [[Yunginger 2001](#); [Paller 2003](#)]. Reports also exist of subjects with known peanut allergy who have continued to safely use products such as Derma-Smoothe/FS even after an anaphylactic reaction to peanuts [[Paller 2003](#)]. The refined peanut oil used in the Derma-Smoothe/FS, DermOtic, and miconazole oil products has been treated to remove the peanut proteins which are generally responsible for allergic reactions to peanuts. Thus, the inclusion of subjects with peanut allergy in this study is not expected to pose an excessive risk to these subjects.

## 2 OBJECTIVES AND RATIONALE

The objectives of the study are to:

- Obtain preliminary evidence of the efficacy and safety of miconazole oil compared with vehicle over a 14-day treatment duration.
- Descriptively compare the efficacy and safety of miconazole oil over treatment durations of 7 versus 14 days.

### 3 STUDY DESIGN

This study is a randomized, partially masked, multiple-dose, parallel-group design study conducted at up to 10 study centers in the US. Approximately 75 male or female subjects with otomycosis will receive study drug. Subjects will be randomly assigned in a 1:1:1 ratio to receive miconazole oil [administered as 5 drops per ear at ~30 mg per drop instilled into the external ear canal of the ear(s) affected by otomycosis] for 7 or 14 days, or vehicle for 14 days. Interim assessments are planned to ensure that there is a sufficient number of subjects within each group for the primary analysis. If deemed necessary the randomization ratio may be adjusted following the interim assessments; see [Section 10.5.5](#) for details. For subjects assigned to the 14-day treatment duration with either miconazole oil or vehicle, the contents of the study drug will be masked to both the subject and the investigator and study staff (i.e., double-blind), but the treatment duration assigned to each subject (7 or 14 days) will be unmasked to both the subject and the investigator and study staff.

At Screening/Baseline (Day 1), potentially eligible subjects will provide informed consent, and subjects will undergo screening evaluations to include a physical examination, an assessment of the signs and symptoms of otomycosis (pruritus, debris, visual examination for presence of fungal elements, and pain), and an evaluation of medical history. Urine will be obtained for pregnancy screening in female subjects of childbearing potential. Prior and concomitant medications will be reported. Subjects with positive signs and symptoms of otomycosis and who meet all other eligibility criteria will be entered into the study, and a subject global assessment of disease will be performed. Fungal and bacterial cultures of the affected ear(s) will be taken, then debris will be cleaned from the affected ear(s) following the site's normal procedures. The subject will then begin treatment with study drug. The subject or caregiver will instill the first dose of study drug at the site, under the supervision of the investigator or site personnel. Adverse events (AEs) will then be assessed. The subject will then leave the clinic and continue to administer the study drug twice per day as instructed. While in the study, subjects will be instructed to avoid getting water in the ear, to consider drying excessive water in the ear by using a blow dryer, and to place a Vaseline-impregnated cotton ball over the affected ear(s) to help keep water out of the ear while bathing or showering.

All subjects will return to the clinic on Day 8. For subjects randomized to the 7-day treatment duration, this visit will constitute the End of Treatment Visit, with procedures performed as described for that visit below. Subjects randomized to the 7-day treatment duration will not administer study drug on the day of this visit. For all other subjects, for whom this visit will constitute an On Treatment Visit, a clinical evaluation of the signs and symptoms of otomycosis, a subject global assessment, a cleaning of the affected ear(s) (following the site's normal procedures), and an assessment of AEs and concomitant medications will be performed, and these subjects will continue to administer the study drug twice per day, up through Day 14, following the same instructions as provided at the Screening/Baseline Visit on Day 1.

All subjects will return to the clinic on Day 15. For subjects randomized to the 7-day treatment duration, this visit will constitute the Test of Cure Visit, with procedures performed as described for the Test of Cure Visit below. For subjects randomized to the 14-day treatment duration, this visit will constitute the End of Treatment Visit, with procedures performed as described for the

End of Treatment Visit below. Subjects randomized to the 14-day treatment duration will not administer study drug on the day of this visit.

Subjects randomized to the 14-day durations will return to the clinic on Day 22 for the Test of Cure Visit, with procedures performed as described for the Test of Cure Visit below.

Procedures performed at the End of Treatment Visit will include an assessment for clinical signs and symptoms of otomycosis, a subject global assessment, and a fungal culture of the affected ear(s). For subjects randomized to the 7-day treatment duration, subjects will have the affected ear(s) cleaned according to the site's normal procedures at this visit, after the efficacy procedures have been completed. AEs and concomitant medications will also be assessed, and the subject will return all study drug.

Procedures performed at the Test of Cure Visit will include an assessment of clinical signs and symptoms of otomycosis, a subject global assessment, and a fungal culture of the affected ear(s). AEs and concomitant medications will also be assessed. A urine pregnancy test will be performed in women of childbearing potential.

Efficacy assessments will include fungal culture of the affected ear(s), assessments of clinical signs and symptoms of otomycosis, and a subject global assessment. In cases of bilateral otomycosis, both ears will be treated and evaluated by the investigator, but the ear with the worse infection at Screening/Baseline, as assessed by the investigator by taking into account both clinical signs and symptoms and fungal culture results, will be used as the study ear for efficacy analyses. If both ears are determined by the investigator to have the same degree of infection at Screening/Baseline, the left ear will be used as the study ear for the purposes of efficacy analyses.

Safety assessments will include AEs.

### **3.1 Number of Subjects**

Approximately 75 eligible subjects are planned to be enrolled in order to achieve approximately 10 subjects per group (randomized in a 1:1:1 ratio to the 7-day active, 14-day active, and 14-day vehicle treatment groups) with a positive fungal culture at baseline and who have completed the Test of Cure Visit.

### **3.2 Investigators**

The study will be conducted at up to 10 investigative sites located in the US.

The study will be conducted by investigators who are determined by the sponsor to be suitably qualified by training and experience to conduct this study in compliance with all applicable GCP and FDA federal regulations or local regulations. Sub-investigators will be identified on the Form FDA 1572.

### **3.3 Study Duration**

The total duration of the study for a subject from screening until the last visit will be up to 30 days (including the visit window of up to 8 additional days after the scheduled day to complete the final visit).

## 4 STUDY SUBJECTS

### 4.1 Inclusion Criteria

In order to be eligible for the study, subjects must meet all of the following criteria:

1. Male or non-pregnant, non-lactating females
2. Diagnosis of uncomplicated otomycosis of the external ear only, in the ear(s) that will be treated with study drug, with a score for fungal elements of  $>0$  in each ear to be treated with study drug (see [Section 7.4](#) for definitions of the scores for each of the otomycosis signs and symptoms). Subjects must also have at least two of the following signs or symptoms of otomycosis in each ear to be treated with study drug: pruritus,  $>1$ ; debris,  $>1$ ; or pain,  $>0$ .
3. General good health as determined by medical examination and medical history, and who are free of clinically significant disease, including diabetes mellitus that is not well-controlled or that could interfere with the study
4. Females of childbearing potential must have had a negative urine pregnancy test at Screening/Baseline and must agree to use an effective method of contraception (as defined in [Section 8.5](#)) from Screening/Baseline up through the Test of Cure Visit (see [Section 6](#)). Females of childbearing potential include any female who has experienced menarche and who has not undergone successful surgical sterilization (hysterectomy, bilateral tubal ligation or bilateral oophorectomy) or is not postmenopausal (defined as amenorrhea  $>12$  consecutive months). Females who are using oral, implanted, or injectable contraceptive hormones, an intrauterine device (IUD), barrier methods (diaphragm, condoms, spermicide) to prevent pregnancy, practicing abstinence or where partner is sterile (e.g., vasectomy), should be considered to be of childbearing potential
5. Subjects and/or their caregivers (as appropriate for the age of the subject) must have full legal capacity to volunteer
6. Subjects and/or their caregivers must have completed an appropriately administered institutional review board (IRB)-approved informed consent and assent (as applicable) prior to any study related procedures
7. Subjects and their caregivers (as applicable) must agree to comply with all requirements of the protocol
8. For subjects with only one ear meeting all study eligibility criteria, the subject will be eligible for the study, and the ear meeting all eligibility criteria will be treated with study drug and considered to be the study ear for the purposes of study evaluations. In case of bilateral otomycosis in which both ears meet all study eligibility criteria, the subject will be eligible for the study, both ears may be treated with study drug, and the worse ear will be considered to be the study ear for the purposes of study evaluations. If both ears meet study eligibility criteria and are determined by the investigator to have the same degree of infection at Screening/Baseline, the left ear will be considered to be the study ear for the purposes of study evaluations.

## 4.2 Exclusion Criteria

Subjects meeting any of the following criteria will not be eligible for the study:

1. Any other dermatoses or conditions of the ear that may interfere with the evaluation of otomycosis, including concomitant otic infections (including bacterial infection) that require antimicrobial treatment, disease that has spread beyond the external ear(s), or pre-existing skin atrophy of the affected ear(s) that will be treated with study drug
2. Tympanostomy tube or perforated tympanic membrane in the ear(s) that will be treated with study drug
3. History of prior surgery directly affecting and compromising the external auditory canal and/or tympanic membrane of the ear(s) that will be treated with study drug, except for prior tympanostomy tube(s) that have already been removed and completely healed
4. Use of any topical medicated treatments for otomycosis within 14 days of study entry
5. Use of any systemic antifungal therapy within 28 days of study entry, warfarin within 28 days of study entry, immunosuppressive or immune-stimulating drugs within 28 days of study entry, or systemic steroids within 3 months of study entry
6. Fever of  $\geq 100^{\circ}\text{F}$  at study entry
7. Recurrent otomycosis that has been unresponsive to previous antifungal treatment
8. Known hypersensitivity to any of the components in the test formulation
9. Participation in another investigative trial within 28 days of study entry.

## 4.3 Subject Completion

The subject has completed the study when the Test of Cure Visit is completed. Subjects who require further follow-up for an AE will be followed according to [Section 8.4](#).

## 4.4 Subject Discontinuation

A subject MAY be withdrawn from the study (at the discretion of the investigator, sponsor, and/or IRB) prior to study completion for any of the following reasons, including, but not limited to:

- A serious adverse event (SAE) occurring during the course of the study which precludes continued follow-up
- Intercurrent illness which may, in the investigator's opinion, significantly affect study assessments
- Failure to follow required study procedures

A subject MUST be discontinued prior to the final study visit for any of the following reasons:

- Whenever the subject decides it is in his/her best interest to withdraw
- Whenever the investigator decides it is in the subject's best interest to be withdrawn

Prior to discontinuing a subject, every effort should be made to contact the subject, schedule a final study visit, and obtain as much follow-up data as possible. If possible, the assessment schedule for the Test of Cure Visit should be performed, and an effort should be made to collect all study drug.

Due to the time required to obtain fungal culture results from Screening/Baseline, subjects will be enrolled into the study based on a clinical diagnosis of otomycosis (including the visible presence of fungal elements at Screening/Baseline), without a requirement for a positive fungal culture. Subjects who end up with a negative Screening/Baseline fungal culture will not be discontinued from the study, but these subjects will not be included in the primary efficacy analysis. Because the sponsor's goal is to obtain approximately 10 subjects per group who meet both criteria of having a positive fungal culture at Screening/Baseline and completing the Test of Cure Visit, the number of subjects enrolled into the study may be adjusted depending on the rates of negative fungal culture at Screening/Baseline and of discontinuation or loss to follow-up.

Subject discontinuations will be documented clearly on the applicable electronic case report form (eCRF). Subjects who discontinue from the study will not be replaced, but additional subjects may be enrolled and randomized if it appears that approximately 75 subjects is insufficient to meet the sponsor's goal of approximately 10 subjects per group who meet both criteria of having a positive fungal culture at Screening/Baseline and completing the Test of Cure Visit.

#### **4.5 Subjects Lost to Follow-up**

An effort must be made to contact subjects who do not return for scheduled visits, to schedule the visit and/or obtain as much follow-up data as possible. At least three telephone calls must be placed to the subject at the first missed visit, to attempt to get the subject to complete the visit and to gather as much follow-up data as possible. At least three telephone calls must also be placed to the subject for any subsequent missed visits after an attended visit, to attempt to get the subject to complete the visit and to gather as much follow-up data as possible. Subjects who miss a visit may still be scheduled for a subsequent visit. Subjects who cannot be contacted via three telephone calls to schedule a missed visit may be considered lost to follow-up and discontinued from the study.

All follow-up attempts will be documented and kept with the subject's source documentation, and the applicable eCRFs will be completed. The date a subject will be considered lost to follow-up will be the date of the last non-missing visit.

## 5 CONCOMITANT THERAPIES

All concomitant therapies must be recorded on the eCRF. All therapies within 28 days prior to Day 1 must also be recorded on the eCRF.

Every effort should be made to keep concomitant therapy and dosing constant during the study. Any changes in concomitant therapies during the study must be recorded on the eCRF at each visit. The reason for any change in concomitant therapies should be reported as, or in conjunction with, an AE except as noted below:

- Prophylactic therapies, such as vaccines, must be recorded on the eCRF but should not be reported as AEs.
- Changes in therapy for pre-existing conditions that are not related to a worsening of the condition must be reported on the eCRF but should not be reported as AEs. The condition must be reported on the eCRF as part of the subject's medical history.

### 5.1 Permitted Medications

Therapies (medication and non-medication therapies) not restricted by the protocol may be used during the study for the treatment or prevention of disease or to maintain good health. Vitamins and mineral supplements are permitted at dosages considered by the investigator as reasonable for maintaining good health. Non-prohibited chronic therapies being used at Screening/Baseline may be continued.

### 5.2 Prohibited Medications

Other than the study drug, no other topical medications are allowed to be used in the ears. Other prohibited treatments include systemic antifungal therapy, warfarin, immunosuppressive or immune-stimulating drugs, and systemic steroids.

## 6 STUDY SCHEDULE

### 6.1 Study Flow Chart

The study schedule is presented in Table 1.

**Table 1 Study Schedule**

| Evaluations and Procedures:          | Screening/
Baseline
Day 1 | On
Treatment a
Day 8 c | End of
Treatment a
Day 8 or 15 d | Test of
Cure b
Day 15 or 22 e |
|--------------------------------------|---------------------------------|--|--|---|
| Informed consent/assent              | X                               |  |  |   |
| Inclusion/exclusion criteria         | X                               |  |  |   |
| Medical/medication history           | X                               |  |  |   |
| Physical examination                 | X                               |  |  |   |
| Otomycosis signs and symptoms        | X                               | X  | X  | X   |
| Urine pregnancy test f    | X                               |  |  | X   |
| Randomization                        | X                               |  |  |   |
| Dispensation of study drug           | X                               |  |  |   |
| Dispensation of subject diary        | X                               |  |  |   |
| Collection of subject diary          |                                 | X  | X  |   |
| Administration of study drug at site | X                               |  |  |   |
| Weighing of study drug               | X                               | X  | X  |   |
| Collection of study drug             |                                 |  | X  |   |
| Subject global assessment            | X                               | X  | X  | X   |
| Microbial culture g       | X                               |  | X  | X   |
| Ear cleaning                         | X                               | X  | X h   |   |
| AE evaluations                       | X                               | X  | X  | X   |
| Concomitant medications review       | X                               | X  | X  | X   |

- a. This visit may occur up to 3 days later than the specified day.
- b. This visit may occur up to 1 day sooner or up to 8 days later than the specified day.
- c. For subjects randomized to the 14-day durations, the Day 8 visit constitutes an On Treatment Visit; for subjects randomized to the 7-day group, the Day 8 visit constitutes the End of Treatment Visit with those procedures performed instead
- d. The End of Treatment Visit is scheduled to occur on Day 8 for subjects randomized to the 7-day treatment duration, and on Day 15 for subjects randomized to the 14-day treatment durations
- e. The Test of Cure Visit is scheduled to occur on Day 15 for subjects randomized to the 7-day treatment duration, or on Day 22 for subjects randomized to the 14-day treatment durations. In case of early termination, the assessments planned for the Test of Cure Visit should be performed if possible
- f. Females of childbearing potential only
- g. For both fungi and bacteria at the Screening/Baseline visit and for fungi only at the End of Treatment and Test of Cure visits
- h. To be performed in subjects randomized to the 7-day group only, and after all efficacy assessments (otomycosis signs and symptoms, subject global assessment, and microbial culture) have already been performed

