The mechanisms of action of miconazole when used topically for the treatment of fungal infections involve its actions against the fungal organisms, rather than their human host. Miconazole targets the cytochrome P450-dependent enzyme 14- $\alpha$ -sterol demethylase, an enzyme that is also involved in mammalian cholesterol synthesis, resulting in inhibition of ergosterol biosynthesis in the cell membrane. Because ergosterol is an important component of the cell membrane, inhibition of its synthesis inhibits fungal cell growth [Vandenbosch 2012]. In addition to its activity toward the enzyme 14- $\alpha$ -sterol demethylase, miconazole also leads to increased reactive oxygen species in fungal organisms, which appears to result in fungicidal activity [Vandenbosch 2010; Musaji 2010].

The mechanisms of action of miconazole against fungi in general appear to be applicable to fungi associated with otomycosis, in that miconazole has been demonstrated to have activity against some clinical isolates of fungi associated with human otomycosis in the US *in vitro* [Bassiouny 1986; Stern 1988]. Clinical studies of 2% miconazole conducted outside of the United States also suggest the efficacy of miconazole in the treatment of human otomycosis [Kiakojuri 2007; Vennewald 2010; Navaneethan 2015].

The purpose of this study is to gather preliminary data on the efficacy and safety of 2% miconazole oil after topical otic administration in subjects with otomycosis. A 14-day regimen of

twice-daily administration of 2% miconazole oil will be descriptively compared with the same treatment regimen using the product vehicle. Furthermore, the 14-day regimen of 2% miconazole oil will be compared with a 7-day regimen, to gather preliminary dose-ranging data regarding the duration of treatment. The 2% concentration of miconazole is selected for this study due to the results of an internal study conducted by the sponsor *in vitro* demonstrating greater zones of inhibition against *Candida* and *Aspergillus* using the 2% concentration compared with the 1% concentration. Furthermore, the 2% miconazole concentration is commonly used for dermatophyte infections, and topical application is expected to be  $\geq 1000$ -fold the minimum inhibitory concentrations (MICs) of the *Candida* and *Aspergillus* organisms most commonly associated with human otomycosis in the US.

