### 6.2.1 Screening / Baseline

Screening procedures will occur prior to randomization and will include:

- Informed consent and assent (as applicable)
- Medical history
- Prior and concomitant medications
- Physical examination
- Urine pregnancy test (in female subjects of childbearing potential only)
- Otomycosis signs and symptoms
- Determination of subject eligibility for the study

Subjects who are eligible for the study will undergo the following additional procedures:

- Subject global assessment
- Microbial culture (fungi and bacteria)
- Ear cleaning
- Randomization
- Weighing of study drug, followed by dispensation of study drug to subject
- Dispensation of subject diary to subject.
- Administration of the first dose by the subject or caregiver under the supervision of the investigator or other study personnel
- Collection of AE information, with the time of AEs to be reported as occurring either before or after the first dose of study drug
- Subject instruction about the date on which they are to stop administering study drug (after all doses have been administered on Day 7 for the 7-day group, and after all doses have been administered on Day 14 for the 14-day groups; subjects will be instructed that study drug should be stopped on the appropriate date regardless of the date for which the next visit is scheduled)

- Subjects will be instructed to bring their bottle of study drug and the diary to the site for their next visit

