### **6.2.2 On Treatment**

These visits may occur up to 3 days later than the specified day. Subjects randomized to the 7-day group will not have any On Treatment visits and will instead proceed directly to the procedures specified for the End of Treatment Visit. Subjects randomized to the 14-day groups will have one On Treatment visit on Day 8.

Subjects will be instructed not to administer any study drug on the day of this visit until after the visit has occurred, if the visit is scheduled for the morning. If the visit is scheduled for the afternoon, subjects will be instructed that the morning dose of the study drug can be administered prior to the visit.

The following procedures and evaluations will occur during the On Treatment visits:

- Otomycosis signs and symptoms
- Subject global assessment
- Ear cleaning
- AE evaluation
- Review of concomitant medications
- Weighing of study drug and return of the bottle of study drug to the subject
- Review of subject diary.
- Subject reminder to continue to administer their assigned study drug twice daily up through the date on which they are to stop administering study drug (after all doses have been administered on Day 14; study drug should be stopped on the appropriate date regardless of the date for which the next visit is scheduled)
- Subjects will be instructed to bring their bottle of study drug and the diary to the site for their next visit

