### **6.3 End of Treatment**

This visit may occur up to 3 days later than the specified day. Subjects randomized to the 7-day group will have the End of Treatment Visit on Day 8, and subjects randomized to the 14-day groups will have the End of Treatment Visit on Day 15.

The following procedures and evaluations will occur during the End of Treatment visits:

- Otomycosis signs and symptoms
- Subject global assessment
- Microbial (fungal) culture
- Ear cleaning (in subjects randomized to the 7-day group only)
- AE evaluation
- Review of concomitant medications
- Collection of subject diary
- Collection/weighing of study drug

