### **6.4 Test of Cure**

This visit may occur up to 1 day sooner or up to 8 days later than the specified day. Subjects randomized to the 7-day group will have the Test of Cure Visit on Day 15, and subjects randomized to the 14-day groups will have the Test of Cure Visit on Day 22.

The following procedures and evaluations will occur during the Test of Cure Visit:

- Otomycosis signs and symptoms
- Subject global assessment
- Microbial (fungal) culture
- AE evaluation
- Review of concomitant medications
- Urine pregnancy test (in female subjects of childbearing potential only)

In case of early termination, the procedures planned for the Test of Cure Visit should be performed if possible.

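### Does the 7-day arm's ear cleaning after its last dose undermine the 7-versus-14-day comparison?

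*Protocol*

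**What the plan says.** Protocol section 3 has all affected ears cleaned on Day 1, after the baseline cultures. The next cleaning is at the Day 8 visit, which has a different name in each arm. For the 14-day arms it is an ordinary mid-treatment visit: "Subjects randomized to the 14-day groups will have one On Treatment visit on Day 8" (section 6.2.2), with cleaning on its list of procedures. For the 7-day arm it is End of Treatment, and footnote h of Table 1 places the cleaning there: "To be performed in subjects randomized to the 7-day group only, and after all efficacy assessments". Section 6.3 agrees. No cleaning is scheduled at Test of Cure.

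Section 6.2.1 fixes the end of dosing regardless of visit date: "after all doses have been administered on Day 7 for the 7-day group, and after all doses have been administered on Day 14". The later of these two dates applies to both longer arms. Test of Cure is Day 15 or Day 22, and section 6.4 adds "This visit may occur up to 1 day sooner or up to 8 days later than the specified day".

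Therapeutic cure (Protocol 10.1.1, SAP 5.1.1) needs a negative culture and a zero score for pruritus, debris, fungal elements and pain.

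Section 1.1 gives the purpose of the 7-versus-14-day contrast as "to gather preliminary dose-ranging data regarding the duration of treatment". The second objective is to "Descriptively compare the efficacy and safety of miconazole oil over treatment durations of 7 versus 14 days". Protocol 10.2 and SAP 6.1 rule out formal hypothesis tests.

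**The concern.** Debris is a component of the primary endpoint, and under Protocol 7.4.2 even scant debris scores 1, which is a failure. Cleaning removes debris. If the two active arms reach Test of Cure at different distances from their last cleaning, a difference in cure could partly reflect that interval and not the extra week of drug.

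The documents describe the contrast in terms of duration, and SAP 6.1.9 even mentions a dose-response relationship. Neither document says that the timing of cleaning limits the reading. At stake would be the second objective: a reader might credit or discount a longer course for a reason that has nothing to do with the drug.

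**Working it through.** The documents give no figure to reproduce here, so the check is visit-day arithmetic.

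Inputs: last dose on Day 7 or Day 14 (Protocol 6.2.1); Day 8 visit allowed up to 3 days late, so Day 8 to 11 (Table 1, footnote a); Test of Cure on Day 15 (14 to 23) or Day 22 (21 to 30), from the window of 1 day early to 8 days late (footnotes b and e). Ranges in brackets use these windows.

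| Quantity | 7-day arm | 14-day arms |
|---|---|---|
| Scheduled cleanings | 2 | 2 |
| Second cleaning minus last dose | 8 − 7 = +1 (to 11 − 7 = +4) | 8 − 14 = −6 (to 11 − 14 = −3) |
| Doses after that cleaning | 0 | Day 8: 2 × (14 − 8 + 1) = 14, or 13; Day 11: 2 × (14 − 11 + 1) = 8, or 7 |
| Test of Cure, days since cleaning | 15 − 8 = 7 (14 − 11 = 3 to 23 − 8 = 15) | 22 − 8 = 14 (21 − 11 = 10 to 30 − 8 = 22) |
| Test of Cure, days off drug | 15 − 7 = 8 (7 to 16) | 22 − 14 = 8 (7 to 16) |

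The lower dose count in each pair applies when the morning dose precedes an afternoon visit (Protocol 6.2.2).

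**Why the intervals differ.** Test of Cure is 8 days after the last dose in every arm, and the second cleaning is nominally on Day 8 in every arm. Days from cleaning to Test of Cure are therefore (last dose day + 8) − 8, which equals the last dose day: 7 or 14. The 7-day gap is the difference in duration itself. Footnote h does not add a cleaning; without it the 7-day arm would have one against two.

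**Could everything be matched?** Purely as arithmetic, not as a suggestion: with no Day 8 cleaning in the 7-day arm, time since cleaning would match (15 − 1 = 14 and 22 − 8 = 14), but the number of cleanings would not. With the second cleaning in the 14-day arms on Day 15, time since cleaning would match (22 − 15 = 7), but the arms would no longer be cleaned on the same study days, and the gap between cleanings would be 14 days against 7. Each arrangement gives up one match to gain another.

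**Possible size.** The documents give neither the direction nor the size of any effect of time since cleaning. As an illustration, suppose a share of 0.4 to 0.8 of subjects meets every other component of cure, and a more recent cleaning raises the chance of debris 0 by 0 to 30 points. The 7-day cure rate would then rise by between 0.4 × 0 = 0 and 0.8 × 30 = 24 points. All of these rates are assumed.

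**Precision.** Protocol 3.1 aims for about 10 evaluable subjects per group. The 95% half-width for a difference is 1.96 × √(2p(1 − p)/10): 35.1 points at an assumed p of 0.2 or 0.8, and 43.8 points at 0.5. Even the largest illustrated shift lies inside that width.

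**The case for a change.** The best case for a change is that imprecision and attribution are separate limits, and more subjects would cure only the first. In a study without tests, the written interpretation is all that the second objective yields, so its wording matters. A sentence in SAP 6.7.1 and a table footnote would cost almost nothing.

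The facts behind this stand: the order of last dose and cleaning is opposite in the two arms throughout the visit windows, and neither document names it as a limit. The need for a change does not follow.

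- The sentence in Protocol 1.1 that mentions duration calls each course a regimen and the data preliminary. Nowhere do the documents claim to isolate duration. The remark in SAP 6.1.9 is a reason for excluding major deviations, not a statement about Test of Cure.
- The reader can already see the relevant facts. SAP 6.7.1 gives the two Test of Cure days; Tables 14.2.2.3 to 14.2.2.7 show culture and each sign by arm and visit, in both the MITT and per-protocol populations; and Listing 16.2.5.1 records ears cleaned.
- A footnote confined to cleaning and study day would be a partial list. Duration is unmasked (Protocol 3), while pruritus and pain are scored by the investigator. SAP 6.1.6 removes the 7-day kits at the interim allocation assessment, so 14-day subjects enrolled later have no concurrently randomised 7-day counterparts. Naming some limits and not others could reassure wrongly.
- The End of Treatment rows are not a cleaner contrast. Nominally both arms are then 7 days since cleaning and 1 day off drug, but after one cleaning versus two, and on Day 8 versus Day 15.

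**Conclusion.** The observation is correct, but it is a limit on interpretation and not a fault in the plan. The arms share the same two scheduled cleanings. Different intervals to Test of Cure (7 versus 14 nominal days) follow from comparing two durations at a common 8 days off drug, and removing that difference would create another. The choice is a fair trade-off.

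A difference between the active arms should be read as a difference between regimens. A careful study report would say so for the MITT and per-protocol results alike, and would mention the unmasked duration and the removal of 7-day kits in the same place. That is ordinary reporting judgement; the analysis, tables, missing-data rule and schedule need no amendment.

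This rests on the comparison remaining descriptive, as both documents state, and on about 10 evaluable subjects per group. A later claim that duration alone explains a difference would need a different design. Miconazole versus vehicle at 14 days is untouched, because those arms follow one cleaning schedule.
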